### 9.4.2 Secondary Endpoint

1 year overall survival status: Overall survival (OS) is defined as the duration from date of registration to date of death due to any cause. Patients last known to be alive are censored at date of last contact.

### **9.4.3 Exploratory Endpoints**

1. Patterns of radiographic response and progression in the thorax, brain, and other sites from the time of small cell lung cancer diagnosis until study conclusion.
2. Patterns of radiographic response and progression within and outside the radiation treatment field from the time of small cell lung cancer diagnosis until study conclusion.

## **9.5 Analyses**

### **9.5.1 Demographics and Baseline Characteristics**

Demographics and baseline laboratory results will be summarized using descriptive statistics for all participants.

### **9.5.2 Efficacy Analyses**

At the PFS analysis time point, primary PFS analyses will be conducted. The PFS curve, PFS median with 95% CIs, and PFS rates at 6 and 12 months with 95% CIs will be estimated using Kaplan-Meier methodology.

At the OS analysis time point, the OS analyses will be conducted. OS curves, OS medians with 95% CIs, and OS rates at 12 and 24 months with 95% CIs will be estimated using Kaplan-Meier methodology.

Additionally, at the same time point as the primary OS analysis, PFS curves, PFS medians with 95% CIs, and PFS rates at 6 and 12 months with 95% CIs will be estimated using Kaplan-Meier methodology.

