## 1.1 Study Rationale

### 1.1.1 Rationale for Investigating First-Line Maintenance Therapy in SCLC

SCLC accounts for 15 to 20% of new cases of lung cancer and is associated with poor outcomes. SCLC is traditionally classified as Limited Stage Disease (LD-SCLC: TNM stages I to IIIB) and Extensive Stage Disease (ED-SCLC: TNM stage IV with distant metastases (M1) including malignant pleural effusions). For LD-SCLC, a combined therapeutic approach of radiotherapy, chemotherapy and (rarely) surgery is used with curative intent[1]. Most patients at diagnosis have ED-SCLC and are treated with four to six cycles of etoposide plus platinum-based therapy (EP), which remains the standard chemotherapy regimen for LD- and ED-SCLC[2]. Overall survival (OS) remains poor with median survival for LD-SCLC at 18 to 30 months[3] and for ED-SCLC in the range of 9 to 12 months[4-7]. Despite high initial response rates, in particular in patients with ED-SCLC, the disease does recur or progress rapidly after completion of chemotherapy, with median PFS of only 2-3 months[7, 8]. A Dutch randomized phase III of patients with ED-SCLC treated with thoracic radiation therapy following EP reported a significant improvement in PFS at 6 months (24% vs 7%, HR 0.73) and a significant improvement in 2 year OS (13% vs 3%, p=0.004) with the addition of thoracic radiation therapy[5]. There are no other established standard of care treatments for subjects with ED-SCLC who complete first line therapy with EP and have achieved stable disease or response. In a phase 3 trial of topotecan versus observation, topotecan did not show an OS prolongation for SCLC patients after completion of EP[8]. Recently, sunitinib showed an improved PFS in a Phase 2 trial of sunitinib vs placebo in SCLC patients after completion of EP[7]. Despite the extensive chemotherapy regimens administered to ED-SCLC patients, approximately 75-90% of patients have persistent intrathoracic disease and though consolidative RT alone to the residual thoracic disease can improve time to progression in the thorax, 2 year OS is still only 13% among patients treated with TRT [5]. This underscores the need for more effective treatment options in this devastating malignancy.

Considering the short median OS for patients who have completed first line platinum-based treatment, as well as the even shorter PFS experienced in this disease, new treatments complementary to SCLC standard first-line platinum-based treatment are required.

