The total duration of the study from start to final analysis of overall survival is expected to be 30 months (18 months of accrual + 12 months of follow-up), assuming an increasing accrual rate from 2 participants/month for the first 6 months, then increasing accrual rate (5 participants/month during 18 months). PFS will be analyzed before OS (Section 9). Additional survival follow-up may continue for up to 5 years from the primary analysis of survival. The study will end once survival follow-up has concluded. Participant safety will be monitored on an ongoing basis as described fully in Section 7.

The start of the trial is defined as first visit for the first participant screened. The end of trial is defined as the last visit for the last participant. Study completion is defined as the final date on which data for the primary endpoint was collected.

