## 9.2 Phase I/II Sample Size Determination

We propose a single arm, non-randomized phase I/II study, with the goal to evaluate efficacy compared to historical controls. Slotman et al. [5] reported a 6-month progression-free survival (PFS) of 24% with platinum-based chemotherapy and thoracic radiation therapy. We would propose to pursue a phase III randomized controlled study if there is a 20% improvement in 6-month PFS with the addition of combined immune checkpoint blockade as part of the proposed clinical study. Therefore, this regimen would be considered not worthwhile to pursue if the true 6-month PFS is 24% or less and worth pursuing if the true 6-month PFS is 44% or greater. The trial will use a Simon's 2-stage design[49] with 1-sided 0.05 level type I error and 90% power. The total target sample size is 52 patients. During the 1st stage, 18 patients will be accrued. If 4 or fewer patients have not progressed at 6 months, the study will be closed for futility. However, if at least 5 patients have not progressed at 6 months, then the study will continue to accrue an additional 34 patients. Once the total number of patients has accrued (n=52), then the null hypothesis will be rejected if at least 18 patients have not progressed at 6 months. In order to accommodate censoring, we may increase the total sample size by up to 10% (n=57).

- The final PFS analysis is targeted to occur 6 months after the last participant is enrolled
- The final OS analysis is targeted to occur 1 year after the last participant is enrolled.

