### 9.2.1 Accrual Justification

Fifty patients will be included at phase I/II study completion inclusive of those patients treated as part of the safety lead in. Moffitt Cancer Center in Tampa, FL, will be the primary and lead institution for this phase I/II single arm study. Moffitt sees about 40 patients with ED-SCLC each year, and we estimate that approximately 25% of patients will be eligible for study enrollment. Additionally, we have support to enroll patients at up to 5 additional US academic institutions that see a similar number or more patients with ED-SCLC annually. Accounting for delays in study opening at the onset and for delays due to interim safety and efficacy stopping points as described above, we anticipate completing accrual to our 50-patient study in about 18 months. We expect to accrue approximately 1 or 2 patients per month for the first 6 months, then approximately 4 patients per month for the remaining 12 months.

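### The 24-month OS rate is scheduled for an analysis 12 months after the last enrolment, when about one or two patients would be at risk at 24 months; a later cut-off is a cheap gain in precision

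*Combined protocol and SAP*

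**What the plan says.** - Section 9.5.2, for the OS analysis time point: "OS rates at 12 and 24 months with 95% CIs will be estimated using Kaplan-Meier methodology".
- Section 9.2 fixes that time point: "The final OS analysis is targeted to occur 1 year after the last participant is enrolled". Section 4.2 puts it at 30 months from study start, made up of 18 months of accrual and 12 of follow-up.
- Section 9.2.1 expects "approximately 1 or 2 patients per month for the first 6 months, then approximately 4 patients per month for the remaining 12 months". Section 4.2 gives the upper end of the same early rate, "assuming an increasing accrual rate from 2 participants/month for the first 6 months".
- Section 9.4.2 counts OS from registration.
- The OS objectives in 2.2 are the 1-year rate and the median. The secondary endpoint in 9.4.2 is 1-year OS. The 24-month rate appears only in 9.5.2.
- Section 4.2 adds: "Additional survival follow-up may continue for up to 5 years from the primary analysis of survival". Section 4.6 sets survival visits every 3 months up to 5 years. No OS analysis is scheduled on those later data.

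**The concern.** A patient needs 24 months between registration and data cut-off to be observable at 24 months. With the cut-off 12 months after the last enrolment, only those who entered in the first part of accrual qualify, and the plan expects that part to be slow. The 24-month estimate and its interval would then be read from a stretch of the curve with almost nobody left at risk. One late death can move it sharply, and if nobody is at risk the estimate may be zero or undefined. At stake is the precision of a planned survival figure, when the follow-up that would supply a better one is already specified.

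**Working it through.** **Timeline.** 18 + 12 = 30 months, which reproduces the figure in 4.2. Reaching 24 months by month 30 requires registration by month 30 − 24 = 6.

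**Patients who can have 24 months of follow-up.** Accrual in months 0 to 6 is 6 × 1 = 6 to 6 × 2 = 12.

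The count falls if accrual stops once 52 are enrolled and the cut-off is exactly 12 months later:
- 9.2.1 rates, 1 per month early: 6 + 4 per month gives 52 at 6 + 46/4 = 17.5 months; cut-off 29.5; about 5 patients enrolled by month 5.5.
- 9.2.1 rates, 2 per month early: 6 + 40/4 = 16 months; cut-off 28; 2 × 4 = 8 patients enrolled by month 4.
- 4.2 rates, 2 then 5 per month: 6 + 40/5 = 14 months; cut-off 26; 2 × 2 = 4 patients enrolled by month 2.

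So 6 to 12 is, if anything, generous on the stated rates.

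**Assumptions for precision.** n = 52 (section 9.2), exponential OS, no dropout. The central case has 9 patients in months 0 to 6 (midpoint of 6 and 12) and 43 in months 6 to 18. The documents give no assumed 24-month OS for this regimen, so S = 13% and S = 22% (a median of 11 months) are used as a range.

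**At risk at 24 months, cut-off at month 30.** The expected number is 9 × S, and the chance that nobody is at risk is (1 − S)^9.
- S = 13%: 9 × 0.13 = 1.2 patients; 0.87^9 = 0.29.
- S = 22%: 9 × 0.22 = 2.0 patients; 0.78^9 = 0.11.

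With 6 to 12 early patients in place of 9, the expected number runs from 0.8 to 1.6 at S = 13% and from 1.3 to 2.6 at S = 22%.

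**At risk with the cut-off 24 months after the last enrolment (month 42).** All 52 have the required follow-up: 52 × 0.13 = 6.8 and 52 × 0.22 = 11.4 patients.

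**Standard deviation of the Kaplan-Meier estimate.** Month 30 comes from simulated trials. Month 42 can be checked by √(S(1 − S)/52).

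| True 24-month OS | Month 30 | Month 42 | Formula for month 42 |
|---|---|---|---|
| 13% | 6.9 points | 4.7 points | √(0.13 × 0.87/52) = 4.7 |
| 22% | 8.2 points | 5.8 points | √(0.22 × 0.78/52) = 5.7 |

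A Greenwood calculation with n = 50 and S = 13% agrees: 6.2 to 7.3 points at month 30 for 12 to 6 early patients, against 4.8 with complete follow-up.

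**Slower accrual.** If 52 patients take 24 months, with 18 in the first 12, then 18 can reach 24 months at the planned cut-off. At S = 22%, 18 × 0.22 = 4.0 are at risk, and the standard deviation is about 7.2 points, against 5.7 at the later cut-off.

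**The case against.** **Nothing depends on this rate.** This stands. The historical-control decision in 9.2 concerns 6-month PFS only. A reader might infer that the 24-month rate is meant to be set against the rationale's statement in 1.1.1 that "2 year OS is still only 13% among patients treated with TRT". The documents plan no such comparison. Nor would the later cut-off make it sharp: at a true 22%, 22 ± 1.96 × 5.8 runs from about 11% to 33%, which still includes 13%.

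**Kaplan-Meier uses everyone.** This stands too. A reader might infer that the 24-month estimate rests on a handful of early patients, mostly the safety lead-in. It does not. Every patient has at least 12 months of potential follow-up at the cut-off. With exponential survival and S = 22%, the share of deaths before month 24 that fall in the first 12 months is (1 − √0.22)/(1 − 0.22) = 68%. Nine patients alone would give √(0.22 × 0.78/9) = 13.8 points, whereas the actual 8.2 points corresponds to about 0.22 × 0.78/0.082² ≈ 26 fully followed patients. Only the far tail is thin.

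**The accrual schedule is not firm.** Partly stands. The rates in 9.2.1 give 54 to 60 patients in 18 months, not 50. Section 4.2 also mentions 5 per month during 18 months, which does not fit an 18-month total. Enrolment stops after 6 patients until the lead-in is complete. Section 9.2.1 says its 18 months allows for such delays, but slippage would raise the count and shrink the gain, as the 24-month case shows.

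**The data are not lost.** Correct: follow-up can continue for up to 5 years, so a mature rate can be obtained. What is missing is a planned analysis that uses it.

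**Conclusion.** The mismatch between the 24-month rate and the timing of its analysis is in the plan's own text. Its consequence is limited. On the stated accrual, about 6 to 12 patients can have 24 months of follow-up at month 30, with about 1 to 2 at risk if 24-month OS is 13% to 22%. Nobody is at risk in about 29% of trials at 13% and 11% at 22%. The standard deviation is about 7 to 8 points, against 5 to 6 at a cut-off a year later. These sizes rest on n = 52, exponential survival, no dropout and 9 patients in the first 6 months; under 24-month accrual the gap at 22% falls to about 1.5 points (7.2 v 5.7).

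This is a minor, inexpensive gain in precision for a descriptive estimate. It does not affect the primary PFS analysis, 1-year OS or median OS. A reader might infer that the early 24-month figure must be removed. The documents give no reason for that, provided its immaturity is visible.

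**What to change.** In 9.2 and 9.5.2, keep 1-year OS and median OS at 12 months after the last enrolment, and add:

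*The 24-month OS rate will be estimated at an updated cut-off 24 months after the last participant is enrolled, using the survival follow-up in 4.2 and 4.6; any 24-month rate reported at the earlier analysis will be labelled immature and shown with the number at risk.*

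The cost is one sentence and one more data cut, from survival contacts already specified. No patients or visits are added. The downside is that the mature 24-month figure comes a year later.

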### **9.5.3 Safety Analyses**

Safety analyses will be performed for all treated participants. Descriptive statistics of safety will be presented using National Cancer Institute (NCI) Common Terminology Criteria for Adverse Events (CTCAE) version 4.0. All on-study AEs, drug-related AEs, SAEs and drug-related SAEs will be tabulated using worst grade per NCI CTCAE v4.0 criteria by system organ class and MedDRA preferred term. The listings by participant will be produced for all deaths, all SAEs, and all AEs leading to discontinuation of study drug. On-study laboratory parameters including hematology, chemistry, liver function, thyroid function, and renal function will be summarized using worst grade per NCI CTCAE v4.0 criteria.

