## 2. Target Population

- a) Patients with SCLC documented by histology or cytology from brushing, washing, or needle aspiration of a defined lesion, but not from sputum cytology alone;
- b) Participants must have presented at initial diagnosis with extensive-stage disease (defined as Stage IV (T any, N any, M1a/b) per NCCN Guidelines Version 1.2015, AJCC Cancer Staging Manual, 7th Edition, 2010);
- c) Eastern Cooperative Oncology Group (ECOG) Performance Status (PS) 0 or 1 (see <http://ecog-acrin.org/resources/ecog-performance-status> for details)
- d) Participants must have received 4-6 cycles of platinum-based first-line chemotherapy and must have an ongoing response of complete response (CR), partial response (PR), or stable disease (SD) after completion of chemotherapy. Acceptable combinations, as recommended per NCCN guidelines, include cisplatin or carboplatin combined with either etoposide or irinotecan;
  - i) As an exception to the above criterion, participants receiving only 3 cycles of chemotherapy due to toxicity are eligible, if they have an ongoing PR or CR after the 3rd cycle
  - ii) Participants who have received > 6 cycles of platinum-based first-line chemotherapy are not eligible
- e) Participants must initiate study treatment with thoracic radiation therapy  $\leq$  8 weeks (56 days) from the last dose of platinum-based first line chemotherapy;
  - i) Thoracic radiation therapy must not be administered < 3 weeks (21 days) from the last dose of platinum-based first line chemotherapy
  - ii) Ipilimumab/nivolumab study therapy must not be administered < 13 days and not more than 21 days from the last dose of thoracic radiotherapy
- f) Whenever possible, a formalin-fixed, paraffin-embedded (FFPE) tumor tissue block or 10 unstained slides of tumor sample (archival or recent) for biomarker evaluation should be made available and submitted to the central lab for correlative studies;
- g) Patient re-enrollment: This study permits the re-enrollment of a participant who has discontinued the study due to pre-treatment failure (ie, participant has not been treated). If re-enrolled, the participant must be re-consented.

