#### 4.4.2 Exclusion Criteria

##### 1. *Target Disease Exceptions*

- a) Participants with previous brain metastases are eligible provided that they are treated and asymptomatic not requiring steroids or anticonvulsants, and have stable disease at the screening tumor assessment. A 4 week disease stable interval as confirmed by MRI or CT brain w/ contrast (Table 7.4-2) is required after treatment of brain metastases before initiation of thoracic radiation therapy. In addition, subjects must have been either off corticosteroids, or on a stable or decreasing dose of  10 mg daily prednisone (or equivalent).

b) Participants who have received prior chest radiation which at the discretion of the treating radiation oncologist precludes delivery of protocol radiation therapy as outlined in section 5 .

c) Carcinomatous meningitis

d) Pleural effusion that cannot be controlled with appropriate interventions

e) All toxicities attributed to prior anti-cancer therapy must have been resolved to Grade 1 (NCI CTCAE Version 4) or baseline before administration of study drug(s) other than:

i) Patients with toxicities attributed to prior anti-cancer therapy that either are not expected to resolve and/or result in long-lasting sequelae, such as neuropathy after platinum-based therapy, or are not expected to interfere with treatment on study, such as fatigue, alopecia, or grade 2 hematologic toxicity are eligible.

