### *3. Physical and Laboratory Test Findings*

a) Positive test for hepatitis B virus (HBV) using HBV surface antigen (HBVsAg) test or positive test for hepatitis C virus (HCV) using HCV ribonucleic acid (RNA) or HCV antibody test indicating acute or chronic infection

i) Individuals with a positive test for HCV antibody but no detection of HCV RNA indicating no current infection are eligible

b) Known medical history of testing positive for human immunodeficiency virus (HIV) or known medical history of acquired immunodeficiency syndrome (AIDS)

c) Inadequate hematologic function defined by:

i) Absolute neutrophil count (ANC)  $< 1,000/\text{mm}^3$ .

ii) Platelet count  $< 100,000/\text{mm}^3$ , or

iii) Hemoglobin level  $< 8.0 \text{ g/dL}$

d) Inadequate hepatic function as defined by either:

i) Total bilirubin level  $\geq 1.5$  times the ULN (except patients with Gilbert Syndrome, who are excluded if total bilirubin  $\geq 3$  times ULN), or

ii) AST and ALT levels  $\geq 2.5$  times the ULN or  $\geq 5$  times the ULN if liver metastases are present

e) Inadequate pancreatic function as defined by either:

i) Lipase  $> 1.5$  ULN. Participants with lipase  $> 1.5$  ULN may enroll if there are neither clinical nor radiographic signs of a pancreatitis

ii) Amylase  $> 1.5$  ULN. Participants with amylase  $> 1.5$  ULN may enroll if there are neither clinical nor radiographic signs of a pancreatitis

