## 7 STUDY ASSESSMENTS AND PROCEDURES

### 7.1 Flow Chart/Time and Event Schedule

**Table 7.1-1.** Screening Procedural Outline (MCC 18914)A

Procedure	Screening	Notes
Informed Consent	X	Informed Consent may be obtained at any time, provided it is prior to conduct of any study-related procedures. Note that SAEs are collected from the date of consent.
Inclusion/Exclusion Criteria	X	All inclusion/exclusion criteria should be assessed at screening and confirmed prior to study initiation.
Medical History	X	
Prior Systemic Therapy	X	
Safety Assessments		
Physical Examination	X	
Physical Measurements	X	Include Height, Weight, and ECOG performance Status. Within 28 days prior to thoracic RT.
Vital Signs and Oxygen saturation	X	Temperature, BP, HR, and O 2 saturation at rest by pulse oximetry. Obtain vital signs at the screening visit and within 72 hours prior to thoracic RT.
Assessment of Signs and Symptoms	X	Within 28 days prior to initiation of thoracic RT.
Concomitant Medication Collection	X	Within 28 days prior to initiation of Thoracic RT.
Laboratory Tests	X	CBC with differential, chemistry panel including LDH, AST, ALT, ALP, T.Bili, BUN or serum urea level, uric acid, creatinine, Ca, Mg, Na, K, Cl, P, glucose, bicarbonates (optional), albumin, amylase, lipase, TSH (reflex to free T 3 , free T 4 for abnormal TSH result), hepatitis B surface antigen (HBV sAg), and hepatitis C antibody (HCV Ab) within 28 days prior to initiation of thoracic RT. Screening labs done within 72 hours prior to first dose can also be used for on treatment lab purposes at Day 1 dosing.
ECG	X	Within 28 days prior to initiation of thoracic RT.

Pregnancy Test	X	Performed within 24 hours prior to initiation of thoracic RT for WOCBP only (serum or urine - local/site).
Efficacy/Biomarker Assessments		
Radiographic Tumor Assessment	X	Within 28 days prior to initiation of Thoracic RT. ---CT/ Chest-With IV contrast preferred. ---CT/MRI Abdomen-With oral and IV contrast preferred. ---CT/MRI Pelvis-With oral and IV contrast preferred. Only required if patient has known pelvic visceral metastases or bony metastases in the pelvis. ---MRI/CT Brain-with contrast if possible. MRI preferred.

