**Table 7.1-2. On-Treatment Assessments for All Participants, Thoracic Radiation TherapyA,B**

Procedure	Radiation Treatments 1-5	Radiation Treatments 6-10	Notes
	Beginning of Week 1	End of Week 2	
Targeted Physical Examination	X	X	Within 72 hours prior to initiating (Week 1) and after ending (Week 2) thoracic radiation therapy.
Vital Signs and Oxygen Saturation	X	X	Temperature, BP, HR, O 2 saturation at rest by pulse oximetry at rest (also monitor amount of supplemental oxygen if applicable) within 72 hours prior to initiating and after ending Thoracic Radiation Therapy and at any time a participant has any new or worsening respiratory symptoms. These can also be used for screening purposes if appropriate.
Physical Measurements	X	X	Includes Weight and ECOG performance status within 72 hours prior to dosing. These can also be used for screening purposes if appropriate.
Adverse Events Assessment	CONTINUOUS		Assessed using NCI CTCAE v. 4.0. SAEs should be reported within 24 hours through the MCRN protocol outlined in Section 8.1.
Review of Concomitant Medications	X	X	
Extended Laboratory Tests	X	X	Extended on-study local laboratory assessments should be done within 72 hours prior to initiation of thoracic RT (Week 1) and within 72 hours of completing thoracic RT (Week 2). Labs to be collected include CBC with differential, uric acid, BUN or serum urea level, creatinine, Na, K, Ca, Mg, phosphorus, chloride, bicarbonate (optional), amylase, lipase, glucose, AST, ALT, total bilirubin, alkaline phosphatase, LDH.

Thyroid Function Testing	X		TSH (reflex to free T3 and free T4 if abnormal result) to be performed every 6 weeks (+/-1 week) throughout the study.
Pregnancy Test	X		Serum or urine within 24 hours prior to first dose and then at least once every 4 weeks regardless of dosing schedule.
Efficacy Assessments			
Radiographic Tumor Assessment		NA	See Table 7.4-1 and Table 7.4-2 for CT and MRI scan schedule.
Additional Exploratory Biomarker Testing			
Serum, Whole Blood Collection	X	X	See Table 7.5-1 for biomarker sampling schedule.

A Thoracic RT start must be at least 3 weeks but not more than 8 weeks after completion of platinum based chemotherapy
 
BPlease see section 5.2 for details of RT treatment schedule
			

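### The laboratory safety summary takes each patient's worst on-study grade without reference to baseline and leaves on-study undefined, so abnormalities present at entry can be counted and may be read as on-treatment toxicity

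*Combined protocol and SAP*

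**What the plan says.** The rule for laboratory data is the last sentence of Section 9.5.3: "On-study laboratory parameters including hematology, chemistry, liver function, thyroid function, and renal function will be summarized using worst grade per NCI CTCAE v4.0 criteria". The section gives no baseline comparison, shift table or requirement that a value worsen, and it does not define on-study.

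The term appears in the visit schedule. Table 7.1-2, which is headed as on-treatment assessments, says: "Extended on-study local laboratory assessments should be done within 72 hours prior to initiation of thoracic RT (Week 1" and asks for a second set within 72 hours of completing radiotherapy. Table 7.1-1 adds: "Screening labs done within 72 hours prior to first dose can also be used for on treatment lab purposes at Day 1 dosing".

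Baseline laboratory data have their own sentence in Section 9.5.1: "Demographics and baseline laboratory results will be summarized using descriptive statistics for all participants". Baseline is not defined there either.

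The entry criteria allow abnormal values:
- Radiotherapy starts 21 to 56 days after the last platinum dose (Section 4.4.1, item 2e).
- Toxicity from earlier cancer treatment must have resolved to grade 1 or baseline, with exceptions that include toxicities not expected to interfere with treatment, "such as fatigue, alopecia, or grade 2 hematologic toxicity are eligible" (Section 4.4.2, item 1e).
- AST/ALT may be anywhere below 5 x ULN if liver metastases are present (Section 4.4.2, item 3d).
- Patients with lipase or amylase above 1.5 x ULN "may enroll if there are neither clinical nor radiographic signs of a pancreatitis" (Section 4.4.2, item 3e). No ceiling is stated.

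**The concern.** A worst grade taken over a period shows what arose in that period only if patients started it with normal values, or if the starting value is taken into account. Neither condition is met here. A patient who enters with grade 2 anemia and stays there appears in the table exactly like a patient who enters normal and falls to grade 2 on treatment.

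The trial is single-arm, so no control group shows how much abnormality would have been present anyway. Section 1.4 says the study should supply safety data to guide the design of a phase III trial. A laboratory table that mixes entry abnormality with change on treatment is weaker for that purpose, and a reader is likely to take its counts as toxicity of radiotherapy plus nivolumab and ipilimumab.

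**Working it through.** The plan states no figure for this output, so there is nothing to reproduce. The check has three parts.

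**1. Can an entry abnormality reach the table?** There are two routes.
- If on-study carries the sense it has in Table 7.1-2, the sample before the first fraction is itself eligible to be the worst grade. A screening sample can be too, where it doubles as a Day 1 sample under Table 7.1-1.
- If on-study means after the first fraction, an abnormality that persists to any later sample is still recorded at its entry grade or worse.

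The second route does not depend on how the undefined term is read. Defining the window is therefore not enough without a comparison with baseline.

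**2. Does another planned output correct this?**
- Section 9.5.1 gives a group summary at baseline. Two separate group summaries do not show which patients changed.
- The adverse event tables rest on a definition that requires a new or worsening condition (Section 8). Under Section 8.3, however, a laboratory result is captured as an event only if it is clinically significant or meets the SAE definition, leads to interruption or discontinuation of drug, or needs corrective therapy. Those tables do not cover all laboratory grades.
- The protocol uses baseline elsewhere: dose delay for AST, ALT and bilirubin (Section 6.5.3.2), resumption of treatment (Section 6.5.3.3), and recovery of grade 3 immune-related events (Section 9.4.1). The laboratory summary does not.

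**3. How large could it be?** The documents give no prevalence, so q and e below are assumptions.
- q = share of patients at or above a given grade at entry and counted by either route in part 1.
- e = share with a new or worsened value on study, taken as the same whether or not the patient was abnormal at entry.
- N = 52 (Section 9.2; Sections 4.2 and 9.2.1 say 50, which changes the counts slightly and the percentages not at all).

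Shown in the table = q + (1 - q) x e. Carried over without worsening = q x (1 - e) x N.

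For q = 30% and e = 10%:
- Abnormal at entry: 0.30 x 52 = 15.6.
- Newly abnormal among the other 36.4: 0.10 x 36.4 = 3.64.
- Shown: 15.6 + 3.64 = 19.24, and 19.24 / 52 = 37%.
- Worsened among those abnormal at entry: 0.10 x 15.6 = 1.56.
- New or worsened: 3.64 + 1.56 = 5.2, or 10%.
- Carried over: 19.24 - 5.2 = 14.04, which is 73% of those shown.

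| q | e | Shown | New or worsened | Carried over (patients) | Carried over, share of those shown |
|---|---|---|---|---|---|
| 10% | 10% | 19% | 10% | 4.7 | 47% |
| 30% | 10% | 37% | 10% | 14.0 | 73% |
| 50% | 10% | 55% | 10% | 23.4 | 82% |
| 10% | 20% | 28% | 20% | 4.2 | 29% |
| 30% | 20% | 44% | 20% | 12.5 | 55% |
| 50% | 20% | 60% | 20% | 20.8 | 67% |
| 10% | 40% | 46% | 40% | 3.1 | 13% |
| 30% | 40% | 58% | 40% | 9.4 | 31% |
| 50% | 40% | 70% | 40% | 15.6 | 43% |

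**The end of the window is also open.** Table 7.1-5 collects adverse events for 30 days after drug discontinuation, whereas Sections 8.1.1 and 8.2.1 say 100 days. Laboratory tests are scheduled at follow-up visit 1 (35 ± 7 days after the last dose) and visit 2 (80 ± 7 days after visit 1). Visit 2 normally falls at 35 + 80 = 115 days, and at the earliest at 28 + 73 = 101 days. Whether either sample counts depends on an end date that the plan does not give.

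**The case against.** The strongest reply is that this is a descriptive table on which nothing turns. The regimen is judged by the unacceptable-toxicity rule, monthly committee review, the adverse event tables and 6-month PFS. Laboratory changes that matter clinically reach the event tables, which require worsening and show drug-related events separately. The samples will exist, so a shift table could be settled at programming. All of this is true, and it limits the weight of the point. It does not change what the stated rule would produce, and only this output is planned to cover all laboratory grades.

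A reader might also infer four stronger things that the documents do not support:
- *That the plan reports these abnormalities as toxicity of the regimen.* Section 9.5.3 only says that values are summarised; it attributes nothing. The risk lies in how the table is read.
- *That the worst grade definitely includes the pre-treatment value.* Table 7.1-2 is a visit schedule, and Section 9.5.3 does not refer to it. The pre-radiation sample could equally be meant as the baseline of Section 9.5.1. The term is undefined, and no more than that can be said.
- *That the abnormalities are residue of platinum.* The wider AST/ALT limit is tied to liver metastases, and nothing links raised lipase or amylase to chemotherapy. The cause does not matter for the point.
- *That the table is useless.* For hematology, the general requirement of grade 1 or baseline, the named grade 2 exception and the cell-count limits in Section 4.4.2 confine carry-over mostly to grades 1-2. High-grade hematology counts should be little affected. Lipase and amylase are less protected.

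**Conclusion.** The point holds as a defect of a descriptive safety output. Worst on-study grade without a baseline comparison can count abnormalities that were present at entry, eligibility allows such abnormalities, and no other planned table separates them from change on treatment.

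The effect falls mainly on grade 1-2 hematology and on liver and pancreatic enzymes. Its size is unknown. Over the assumed ranges of 10-50% abnormal at entry and 10-40% new or worsened, about 3 to 23 of 52 patients would be carry-over, or 13% to 82% of those shown. These figures follow entirely from the assumptions. The upper end is least plausible for grade 2 values outside hematology, since hematologic toxicity is the only laboratory toxicity named as an example of the grade 2 exception.

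The primary endpoint, the Simon two-stage rule and the toxicity stopping rule do not use this table. The change is worth making because it is a better method than the one stated and costs little.

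**What to change.** Replace the laboratory sentence in Section 9.5.3 with wording that does the following:

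1. Defines baseline for each analyte as the last value before the first radiation fraction, and uses the same definition in Section 9.5.1.
2. Starts the on-study window after the first fraction and states its end. The 30-day period in Table 7.1-5 and the 100-day periods in Sections 8.1.1 and 8.2.1 must be reconciled, and the text should say whether the samples at follow-up visits 1 and 2 count.
3. Reports, for each analyte, a shift table of baseline grade by worst post-baseline grade.
4. Counts a laboratory abnormality as treatment-emergent only if the post-baseline grade exceeds the baseline grade.

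A second shift table, from the value before Cycle 1 Day 1, is optional. It would help separate the radiotherapy period from the drug period, although no stated objective requires it. Table 7.1-3 already schedules that sample within 72 hours before dosing.

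The cost is a few lines of text and some programming. No visit, sample or patient is added. Within the defined window, the worst grade can still be read from the margin of each shift table.
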